## B. SPECIFIC AIMS

**B.1 Primary Aim:** To investigate the feasibility of a 9-week integrative medicine intervention, as assessed by recruitment and retention in patients with Hypermobility Spectrum Disorder (HSD) or Ehlers-Danlos syndromes (EDS).

- Outcome Measures 1: The recruitment rate will be assessed as the number of participants enrolled per month, over the duration of open recruitment. Our goal is to recruit 20 participants within a span of 4 months. Retention rate will be determined as the proportion of participants completing the mid-study or end-of-study visits, with a goal of 75% retention for each study visit.

**B.2 Secondary Aim:** To evaluate the feasibility of and adherence to a prescribed food plan as well as the feasibility of food tracking as a part of a 9-week integrative medicine intervention in patients with Hypermobility Spectrum Disorder (HSD) or Ehlers-Danlos syndromes (EDS).

- Outcome Measures 2: To assess the feasibility of the dietary recommendations, adherence will be assessed using estimated daily dietary intake recorded in *MyFitnessPal*, a food tracker app for mobile devices and computers. The participant's reported macronutrient breakdown will be compared to the prescribed food plan to calculate an adherence score. Participants will also complete a food plan satisfaction survey at baseline, 5, and 9 weeks that will examine any physical side-effects, support needed, and any barriers to adherence, including food costs. The feasibility of food tracking will be measured by adherence to the recommended use of the app. A threshold of 3 days of reporting per week (including breakfast, lunch, dinner, and snacks) for the 9-week duration of the study will be considered adherent and should provide sufficient data to assess the observance of the recommended food tracking.

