#### MyFitnessPal

#### **Protocol**

Study Title: Integrative Medicine for Hypermobility Spectrum Disorder (HSD) and Ehlers-Danlos (EDS) syndromes: A mixed-methods feasibility study (IMforHSDandEDS)

PI: [name]

IRB #: DH10320/PRAF

Approval Date: 03.03.21

Version: 3.0

*MyFitnessPal*, a food tracker available on both Apple and Android for mobile devices, as well as both Windows and Mac computer platforms, will be used to collect estimated daily dietary intake for participants. *MyFitnessPal* has a database of nutritional information for over 11 million foods that will allow participants to capture their general diet by manually adding individual ingredients, barcode scanning, or finding whole meals. In a comparison of micronutrients and calories between diet-tracking apps and the USDA database, *MyFitnessPal* was shown to have the best coding accuracy. Self-reported data, however, may be subject to inaccuracies. When foods are entered into the *Diary* feature located in the app, the *Nutrient Dashboard* displays daily calories, as well as macronutrient proportions, broken down into carbohydrates, fats, and protein.

Participants will be encouraged to track their daily diet to the best of their ability, and for weeks that there is missing data, a threshold of no less than 3 days of tracking (including breakfast, lunch, dinner, and snacks) per week for the 9-week study duration will be considered adherent and averaged appropriately. Individuals with previous disordered eating patterns, or discomfort with food tracking, will be able to opt-out; however, they will still be shown how to use *MyFitnessPal* to analyze dietary composition for adherence. A 1-week lead-in prior to introducing the food plan will be utilized to provide a baseline record of the participant's general diet. *MyFitnessPal* data will allow us to track general adherence to dietary changes, the overall quality of the participant's diet, and average macronutrient proportions. By measuring the participant's reported macronutrient percentage scores and comparing them with the prescribed food plan, we will be able to calculate an adherence score.

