### Secondary Outcome measures:

#### *Dietary Adherence/Food Tracking Feasibility (MyFitnessPal food tracking):*

- Dietary adherence will be measured by self-reported food tracking through Daily Nutrition Goals in the *MyFitnessPal* app and will be documented at 5 and 9 weeks through the Friends feature. Daily macronutrient contributions will be obtained as percentages of total intake. The suggested macronutrient breakdown for the food plan is 40-50% calories from a carbohydrate source, 35-40 % calories from fat, and 15-20% calories from protein. Weekly recorded consumption of the participant will be compared to this standard for an adherence score. For each of the three macronutrient categories, we will give 2 points if the percentage is within the required range and 1 point if the percentage is within 5% of the required range (maximum 6 points total). A score of 4 and above will be considered adherent to the food plan.
- The feasibility of food tracking will be measured by adherence to the recommended use of the app. A threshold of 3 days of reporting per week (including breakfast, lunch, dinner, and snacks) for the 9-week duration of the study will be considered adherent and should provide sufficient data to assess the observance of the recommended food tracking.

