### **E.9 Statistical Analysis**

All measures collected in the study, including baseline characteristics and outcome measures, will be summarized using mean and SD (biomarkers, anthropometrics), median and IQR (Beighton score), or percentage within each level, for categorical variables. All statistical analyses will be performed at the National University of Natural Medicine.

For Specific Aim 1,

Feasibility of the 9-week integrative medicine intervention will be measured through recruitment and retention at each follow-up visit. Recruitment rate will be presented as the mean number of participants enrolled per month, with enrolment ceasing either after 4 months, or when n=20 participants have been enrolled. Retention will be calculated as the percentage of enrolled participants from whom follow-up data is obtained, at either the 5-week or 9-week visit.

For Specific Aim 2,

Adherence to the recommended diet will be assessed in different ways and tracked by macronutrient levels and dietary composition. In particular, we will assess:

- Percentage of days on which the diet recommendations were met; in order to satisfy this requirement, macronutrient distribution must meet all of the following:
  - Carbohydrates between 40-50%
  - Protein between 15-20%
  - Fat between 25-30 %
- Number of weeks in which recommendations were met at least 5 days;
- Whether recommendations were met on at least 75% of total days (Y/N)
- Mean of weekly adherence scores calculated over the 9-week study period.

Percentage of days and weeks adherent will be summarized across participants as median/IQR/range. We will also present the percentage of participants who met the threshold of 75% days adherent.

Feasibility of the 9-week integrative medicine intervention will also be measured through self-reported food plan satisfaction surveys that assess any negative outcomes, overall cost-prohibitiveness or

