### **Protocol**

Study Title: Integrative Medicine for Hypermobility Spectrum Disorder (HSD) and Ehlers-Danlos (EDS) syndromes: A mixed-methods feasibility study (IMforHSDandEDS)

PI: [name]

IRB #: DH10320/PRAF

Approval Date: 03.03.21

Version: 3.0

burden, support needed, and any barriers that are encountered with the recommended dietary modifications.

- Because these measures are reported as open responses, they will be thematically summarized for representative quotes, at each time point measured.

Adherence with dietary tracking will be assessed by:

- Percentage of total days on which dietary intake was documented. Self-reporting of daily dietary intake on at least 50% of total days will be considered adherent.
- Number of weeks on which intake was self-reported at least 3 days.

For Specific Aim 3,

We will test whether the integrative medicine education intervention reduced pain and improved health-related quality of life in patients with HSD or EDS. VAS pain scores and PROMIS-29 domain scores will be summarized across participants and time points as mean (SD).

Analysis of pain and HRQoL outcomes for Aim 2 will use paired t-tests to assess mean changes unless investigation of distributions indicates a need for nonparametric testing, in which case changes will be analyzed using Wilcoxon signed-rank tests.

For Exploratory Aim 1,

Any associations between pain, HRQoL, and diet will be assessed both cross-sectionally and longitudinally over the course of treatment. Cross-sectional associations of VAS pain score, PROMIS-29 domain scores, and dietary composition measures will be analyzed using Pearson correlations (or Spearman correlations for badly non-normal data). To assess associations of longitudinal changes, we will compute changes in each measure both from baseline to 5 weeks, and from baseline to 9 weeks, and we will similarly evaluate correlations between the changes over each time period.

Cross-sectional correlations assess the association of participants' ordinary diet with pain and health-related quality of life, while correlations of changes assess the association of dietary changes, in response to the treatment recommendations, with changes in pain and HRQoL over the same time frame.

We will also assess associations between age, race, sex, baseline symptoms, and changes in outcomes at follow-up, using Pearson correlations and independent t-tests, as appropriate.

For Exploratory Aim 2,

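### E.9's weekly count of at least 5 on-plan days can never credit a week logged on 3 or 4 days, so it mixes non-logging with non-adherence

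*Combined protocol and SAP*

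**What the plan says.** **Diet adherence (E.9, Specific Aim 2).** The unit is the day: "Percentage of days on which the diet recommendations were met; in order to satisfy this requirement, macronutrient distribution must meet all of the following", followed by ranges for carbohydrate, protein and fat. Three further measures follow: "Number of weeks in which recommendations were met at least 5 days", then "Whether recommendations were met on at least 75% of total days (Y/N)", then the mean of the weekly adherence scores. Days and weeks adherent are summarised across participants by median, IQR and range.

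**Tracking adherence.** E.6 sets "A threshold of 3 days of reporting per week (including breakfast, lunch, dinner, and snacks) for the 9-week duration of the study" as adherent. Section B (Aim 2) gives the same threshold and adds that it "will be considered adherent and should provide sufficient data to assess the observance of the recommended food tracking". E.5, under MyFitnessPal, deals with weeks that have missing data: it requires "a threshold of no less than 3 days of tracking (including breakfast, lunch, dinner, and snacks) per week" and says that such weeks are averaged. E.9 has two tracking measures: documentation on at least 50% of total days, and "Number of weeks on which intake was self-reported at least 3 days".

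**Data source.** E.6 measures dietary adherence by self-reported tracking in the app. No other source of daily intake is described.

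No section says how an unlogged day enters the 5-day count, or whether total days means calendar days or logged days.

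**The concern.** The tracking rules and the weekly diet rule use different minimum numbers of days. Tracking is satisfied by 3 logged days in a week; the diet measure needs 5 on-plan days in that week. A day can be shown to be on plan only if it was logged, so a week with 3 or 4 logged days passes the first rule and is barred from the second before its contents are examined.

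Aim 2 asks two separate questions: can participants follow the food plan, and can they keep up food tracking? For anyone logging fewer than 5 days a week, this measure answers the second under the label of the first. With at most 20 participants summarised by median and range, a few light loggers could pull the reported number of adherent weeks down, and a reader could take tracking burden for difficulty with the diet.

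**Working it through.** The plan derives no figure on this point. The 3-day, 5-day, 50% and 75% cut-offs are simply stated, so there is nothing to reproduce. The check is direct.

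**Step 1: what a week can score.** With L logged days, the number of days shown to be on plan is at most L. The measure requires 5.

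| Logged days L | Accepted as tracked (L ≥ 3) | Can reach 5 on-plan days |
|---|---|---|
| 3 | yes | no |
| 4 | yes | no |
| 5, 6 or 7 | yes | yes |

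This needs no assumption about eating or logging.

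**Step 2: a participant who meets every tracking rule.** Take 4 logged days in each of 9 weeks, every logged day on plan.

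- Study days: 9 × 7 = 63. Logged: 9 × 4 = 36, and 36/63 = 57.1%.
- 3-day weekly rule: met in 9 of 9 weeks.
- 50% rule on calendar days: 0.50 × 63 = 31.5, so 32 days are needed; 36 meets it.
- 5-day diet measure: 4 < 5 every week, so 0 of 9 weeks.
- 75% rule: if total days means calendar days, 0.75 × 63 = 47.25, so 48 days are needed and 36 fails. If it means logged days, 36/36 = 100% and it passes. The answer turns on a definition that the plan does not give.

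It is unclear whether the 1-week lead-in lies inside the 9 weeks. With 8 on-plan weeks the pattern is the same: 32/56 = 57.1%, 28 days needed for 50%, and 0 of 8 weeks.

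**Step 3: how many weeks could be affected.** The documents give no logging rate. Assume each day is logged independently with probability q and every logged day is on plan. The share of accepted weeks that fail is 1 − P(X ≥ 5)/P(X ≥ 3), with X ~ Binomial(7, q).

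| Assumed q | P(X ≥ 3) | P(X ≥ 5) | Accepted weeks that fail |
|---|---|---|---|
| 0.50 | 0.773 | 0.227 | 71% |
| 0.70 | 0.971 | 0.647 | 33% |
| 0.80 | 0.995 | 0.852 | 14% |
| 0.90 | 1.000 | 0.974 | 3% |

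These shares isolate the effect of logging. They do not predict the result under E.9's present ranges, because of Step 4.

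**Step 4: a separate defect in the same bullets.** E.9 and E.8 give fat as 25–30%; E.4.4, E.5 and E.6 give 35–40%. With carbohydrate 40–50% and protein 15–20%, the E.9 upper limits sum to 50 + 20 + 30 = 100. Three shares that total 100% therefore satisfy E.9 only at exactly 50/20/30: one whole-number combination, against 36 with fat at 35–40%. As written, almost no logged day could count as met, however often a participant logs.

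**The case against.** **The 5-day count may be deliberately conservative.** Participants are encouraged to log daily, so 5 days is attainable; E.9 says adherence will be assessed in several ways; and the 3-day threshold was set to judge tracking, not diet. Much of this stands. Counting only demonstrated on-plan days is legitimate. But the plan does not say that unlogged days count as failures, and E.5's averaging of partly logged weeks points the other way. Averaging can serve a weekly mean or the 0–6 score; it does not tell the analyst how to treat a count of days.

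**Low logging will be visible.** E.9 also reports tracking days and weeks, so a careful reader could see the cause. That softens the problem, but does not separate the two quantities within the measure.

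**Stronger readings that the documents do not support.**

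- A reader might take a participant logging 3 days every week as fully compliant with tracking yet scoring 0 weeks. On calendar days, 27/63 = 42.9% misses E.9's 50% rule. The 4-day logger is the sound example.
- A reader might infer that one week could score 6 of 6 on the weekly score and still fail here although every logged day was on plan. A day that meets E.9 has fat of at most 30%, so the E.6 fat item (35–40%) earns at most 1 point and the weekly maximum is 5. That contrast comes from the fat-range conflict, not from logging.
- A reader might infer that Aim 2 would wrongly declare the food plan infeasible. No feasibility verdict is tied to this measure, and E.6's adherent label rests on a weekly score of 4 or more.
- Five of 7 days every week is 45/63 = 71.4%, below the 75% cut-off. A weekly and an overall cut-off need not coincide, so this is no reason to change the 75%.

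**Conclusion.** The point holds as a defect of definition. Under the stated rule, a week logged on 3 or 4 days cannot count as on plan, although the plan accepts it as adequately tracked. A participant who meets both tracking rules can be reported as 0 of 9 weeks with every logged day on plan. This rests only on the rule being a count and on the app log being the sole source of daily intake.

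The practical size is uncertain. It runs from 71% of accepted weeks at 50% logging to 3% at 90%, on assumed, independent daily logging and perfect eating on logged days. The reach is limited: one of four descriptive measures under a secondary aim, with the weekly score untouched. It deserves correction before analysis because the correction is cheap, not because the trial's conclusions depend on it.

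**What to change.** Change the wording of the Aim 2 part of E.9:

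1. Keep the 5-day count, and label it conservative, with unlogged days counted as not met.
2. Beside it, for weeks with at least 3 logged days, report the percentage of logged days on plan, and the number of weeks at or above one stated fraction of logged days. Show the numbers of valid weeks and logged days with both.
3. Leave the 75% cut-off as it is, but state whether total days means calendar or logged days.
4. Reconcile the fat ranges in E.4.4, E.5 and E.6 with those in E.8 and E.9. Until then no day-level measure, in either version, is meaningful.

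**Cost.** No new data are needed. A logged-day measure can be inflated by logging only good days, and weeks with few logged days are noisier, so both versions should be shown.

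A weekly fraction also does not remove dependence on logging entirely. At 5/7, for example, whole days force 3 of 3, 3 of 4, 4 of 5, 5 of 6 and 5 of 7, that is 100%, 75%, 80%, 83% and 71%. If each logged day were on plan with probability 0.75 (an assumption), the chances of passing would be 42%, 74%, 63%, 53% and 76%. The percentage of logged days on plan should therefore be the main companion figure, with the week count as its supplement.

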#### **Protocol**

Study Title: Integrative Medicine for Hypermobility Spectrum Disorder (HSD) and Ehlers-Danlos (EDS) syndromes: A mixed-methods feasibility study (IMforHSDandEDS)

PI: [name]

IRB #: DH10320/PRAF

Approval Date: 03.03.21

Version: 3.0

Ehlers-Danlos syndromes (EDS), in order to determine the recruitment potential in this population and to measure the ability of individuals to complete the program. Participants will be prescribed a food plan, and adherence to and feasibility of the food plan will be measured through participant food tracking and a subjective assessment of the food plan in a brief satisfaction survey. This study aims to recruit 20 patients with HSD or EDS and make preliminary observations regarding the effects of integrative medical care on pain reduction and improved quality of life. Participants will be given a 1-week lead-in to track their general diet prior to starting their prescribed food plan, and associations will be recorded between symptom severity and diet as an exploratory analysis. Patient assessment of chronic illness care and living with a chronic illness will also be captured; to assess the experiences of patients with HSD or EDS, as well as their perceptions of previous medical care and patient-centered medicine, and any changes in these attitudes over the course of 9 weeks. Available studies assessing treatments for HSD or EDS provide insufficient evidence for treatment options; this project studies a novel intervention focused on nutrition and self-management counseling, developed in conjunction with a qualified physician, and would allow us to gain valuable information regarding the feasibility of employing the intervention as well as preliminary data on its effect on health outcomes.

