## Protocol

Study Title: Integrative Medicine for Hypermobility Spectrum Disorder (HSD) and Ehlers-Danlos (EDS) syndromes: A mixed-methods feasibility study (IMforHSDandEDS)

PI: [name]

IRB #: DH10320/PRAF

Approval Date: 03.03.21

Version: 3.0

**B.3 Tertiary Aim:** To examine the effect of a 9-week integrative medicine intervention on overall perceived pain and quality of life in patients with Hypermobility Spectrum Disorder (HSD) or Ehlers-Danlos syndromes (EDS).

- Outcome Measures 3: Participants will complete a Visual Analog Scale for Pain (VAS Pain) and a 29-Item profile HRQoL Survey (PROMIS-29) at baseline, 5, and 9 weeks.

In order to better understand the needs of the patient population, we will also address the following exploratory aims, as far as we are able. These aims can be considered to be independent of the effects of treatment.

**B.4 Exploratory Aim 1:** To evaluate any associations between symptom severity, perceived pain, quality of life, and diet among patients with Hypermobility Spectrum Disorder (HSD) or Ehlers-Danlos syndromes (EDS).

- Participants will be given a 1-week lead-in to establish baseline food patterns before starting the prescribed food plan. Associations of dietary composition, patient-reported symptoms, as well as overall perceived pain and quality of life scores will be examined, both cross-sectionally at intake and longitudinally over the 9 weeks of the intervention.

**B.5 Exploratory Aim 2:** To assess the experiences of chronic illness care and living with chronic illness among patients with Hypermobility Spectrum Disorder (HSD) or Ehlers-Danlos syndromes (EDS).

- Outcome Measure 5: Participants will complete a 26-item survey, Patient Assessment of Chronic Illness Care (PACIC+), that evaluates areas of patient self-management within the chronic care model of healthcare. The PACIC+ ascertains attitudes regarding patient-centered care, living with chronic illness, and chronic illness care; it will be completed by participants at baseline and 9 weeks.

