### **E.4 Participant and Procedure Schedule**

#### **E.4.1 Overview**

The study is comprised of 1 in-person screening, 2 follow-up visits, and 2 telephone or email check-in correspondences for additional support. The in-person screening and 2 virtual follow-up visits will take place at the Healthy Living Community clinic. Virtual follow-up study visits will take place via the Zoom video platform utilized by ChARM TeleHealth, a web-based and HIPAA compliant server maintained by the Healthy Living Community clinic and will occur at 5- and 9-weeks post-enrollment.

During the in-office screening, participants will have their joint mobility measured in accordance with the Brighton Scoring System to confirm that they meet the diagnostic criteria for Hypermobility Spectrum Disorder. Participants who are diagnosed using the Brighton criteria and meet other eligibility criteria will then be asked to provide informed consent (E.4.3) and enrolled in the study if willing. The Clinical Investigator will capture a complete and detailed medical history of enrolled participants, discuss family and social support, as well as prescribe a food plan. The CI will also assess the patient's current self-management strategies and provide general behavioral and psychosocial support. During the 2 follow-up visits, the Clinical Investigator will revisit these self-management strategies. As scheduling visits may be difficult at precisely 5 and 9 weeks, we will leave some flexibility for these points in time to accommodate the schedules of the Clinical investigator, the student researcher, and the participants.

At 2 and 6 weeks, the participants will be contacted by the student researcher to answer any questions, provide nutritional and psychosocial support, monitor for any adverse events, and offer solutions to any dietary challenges. Participants will also be assessed at all study visits for any adverse events.

Participants will be asked to complete pain (VAS), and health-related quality of life (PROMIS-29) instruments at baseline, 5, and 9 weeks. Adherence to the dietary recommendations, as well as the feasibility of food tracking will be obtained using *MyFitnessPal*, a food tracker app throughout the 9 weeks. A food plan satisfaction survey will be collected at 5 and 9 weeks. Participants will fill out the

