### **Protocol**

Study Title: Integrative Medicine for Hypermobility Spectrum Disorder (HSD) and Ehlers-Danlos (EDS) syndromes: A mixed-methods feasibility study (IMforHSDandEDS)

PI: [name]

IRB #: DH10320/PRAF

Approval Date: 03.03.21

Version: 3.0

their daily food tracking with the student researcher, and the data will be collected at 5 and 9 weeks. Participants will be given a 1-week lead-in period so that they can adjust to tracking their dietary intake before starting the food plan and will be instructed to contact the student researcher with any questions.

In the event that the baseline visit is conducted virtually, all procedures will be the same, except that the participant will provide medical documentation of a Beighton score of 4 or more, in lieu of a Beighton measurement being obtained at the visit. We will require informed consent prior to capturing this documentation. The participant will be asked to report their own height and weight. All other data will be captured electronically. Any participant who completes the baseline visit remotely will be invited to complete the Week 5 visit in person, if possible; if the Week 5 visit is completed in person, then weight, height, and Beighton score will be confirmed at that visit.

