#### **E.4.5 Check-in #1 (2 weeks)**

Participants will receive a phone call or e-mail from the student researcher that will answer any questions, provide nutritional and psychosocial support, and offer solutions to any dietary challenges. The goal is to provide support with dietary adherence. This will occur 2 weeks after Visit # 1 and will be set up in advance at a time that works for the participant. If the participant is not available, we will send a check-in email and answer any questions, provide nutritional and psychosocial support, and offer solutions to any dietary challenges by email, if requested. The nutrition counseling script contains suggestions for a general healthy eating pattern but is not a part of food plan adherence. (See Appendix 3B)

Participants will be assessed for any adverse events with the following question, "Are you experiencing any new symptoms or side-effects that you may have noticed?" (See Appendix 3B)

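### The mean weekly diet-adherence score in E.9 appears to include the lead-in week before the food plan starts, so it mixes baseline diet with on-plan diet

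*Combined protocol and SAP*

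**What the plan says.** Section E.9, Specific Aim 2, lists four summaries of dietary adherence. The last is the "Mean of weekly adherence scores calculated over the 9-week study period". It is the only one of the four that names a nine-week window.

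The weekly score is defined in E.6 (Secondary Outcome measures). Each of the three macronutrients earns 2 points if its share of intake is in range, or "1 point if the percentage is within 5% of the required range", to a maximum of 6.

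Three sections place a lead-in week ahead of the food plan:

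- Abstract: "Participants will be given a 1-week lead-in to track their general diet prior to starting their prescribed food plan".
- B.4: "Participants will be given a 1-week lead-in to establish baseline food patterns before starting the prescribed food plan".
- E.4.4 (Visit 1): "Participants will be given a 1-week lead-in period so that they can adjust to tracking their dietary intake before starting the food plan".

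The MyFitnessPal part of E.5 likewise treats the lead-in as the baseline record of diet.

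The study clock starts at enrollment. E.4.1 says that the follow-up visits "will occur at 5- and 9-weeks post-enrollment", and E.4.5 says of the first check-in, "This will occur 2 weeks after Visit # 1". Under E.4.8, participants are told at the week-9 visit that the study is over.

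**The concern.** A summary of adherence to a plan should cover the time when participants were asked to follow it. On the stated timing, one of the nine weekly scores comes from a week when they had not yet started. The same week supplies the baseline diet for Exploratory Aim 1, so it would count both as the pre-plan reference and as adherence to the plan.

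The mean would then describe neither period cleanly. Adherence to the food plan is a named secondary feasibility aim (B.2), and section F foresees using the results to shape a larger study. A mean that is partly baseline diet is a poor guide to whether the plan can be followed.

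**Working it through.** The plan gives no adherence figure to reproduce. The check is a timeline followed by simple arithmetic.

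**Timeline**

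1. Tracking starts at Visit 1, when the app is set up (E.4.4).
2. The one-week lead-in comes next, before the food plan (E.4.4, B.4, Abstract).
3. Food-tracking data are collected at 5 and 9 weeks (E.4.4), and those visits are counted from enrollment (E.4.1).
4. The study ends at the week-9 visit (E.4.8), and no later tracking is described.

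Hence 9 weeks in total minus 1 lead-in week leaves 8 on-plan weeks. No section excludes the lead-in from the mean.

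**Formula**

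Let L be the lead-in week's score and M the mean score over the 8 on-plan weeks.

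- Mean as E.9 defines it: (L + 8M)/9.
- Shortfall against the on-plan mean: M − (L + 8M)/9 = (M − L)/9.

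**Numbers**

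The documents do not give L, so it is an assumed range. With M = 4:

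| Lead-in score L (assumed) | Mean by E.9 | Difference from 4.00 |
|---|---|---|
| 0 | 32/9 = 3.56 | −0.44 |
| 2 | 34/9 = 3.78 | −0.22 |
| 3 | 35/9 = 3.89 | −0.11 |
| 4 | 36/9 = 4.00 | 0 |
| 5 | 37/9 = 4.11 | +0.11 |

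The largest understatement needs M = 6 and L = 0: (6 − 0)/9 = 0.67 points.

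**Are such lead-in scores plausible?**

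Two assumed diets, scored on the E.6 ranges (carbohydrate 40-50%, protein 15-20%, fat 35-40%):

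- 60/15/25 (carbohydrate/protein/fat) scores 0 + 2 + 0 = 2.
- 50/16/34 scores 2 + 2 + 1 = 5.

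Both scores are the same whether the 5% margin is read as percentage points or as relative. For fat at 34%, the lower limit is 35 − 5 = 30 on the first reading and 35 × 0.95 = 33.25 on the second. Ordinary-looking diets can therefore fall on either side of an on-plan mean of 4.

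**The case against.** **The timing is inferred.** The design figure (Figure 2) is not available, and E.4.1 allows flexible visit dates. E.5 describes a nine-week program that includes the food plan, and B.4 mentions the lead-in and the nine intervention weeks separately, which leaves room for a 1 + 9 week layout. The calendar also conflicts with itself: E.4.7 is headed as a 6-week check-in but is set 2 weeks after Visit 2, which is 5 + 2 = week 7. This stands as a reason for caution. The explicit visit timing still favors the lead-in being week 1, because tracking cannot start before Visit 1 and nothing is planned after week 9. The objection does mean that a fix should be tied to the start of the food plan and not only to week numbers.

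**The direction is unknown.** A reader might infer that E.9 will understate adherence. The documents do not support that as a general statement, because they give no lead-in score. The plan is prescribed and its materials are handed out at Visit 1, so some participants may change their diet during the lead-in, which narrows the gap. What stands is that the mean is aimed at the wrong period, with an error of unknown sign.

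**Participants might be misclassified.** E.6 says, "A score of 4 and above will be considered adherent to the food plan". A reader might apply that cut to the nine-week mean and conclude that the lead-in can turn an adherent participant into a non-adherent one. In context the cut belongs to the weekly score, and E.9 sets no cut for the mean.

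**The other measures might be diluted too.** A reader might extend the point to the percentage of days and the 75% rule. E.9 does not define their denominators, so dilution cannot be shown from the text. Counting an extra week cannot lower the number of weeks with at least 5 adherent days.

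**The stakes are low.** This is one of four descriptive diet summaries in a study of up to 20 participants, with no test or decision rule attached. That is correct and limits the weight of the point.

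**Conclusion.** The point holds in limited form. On the stated visit timing, the E.9 mean includes a pre-plan week that the protocol itself uses as baseline, so it does not purely measure adherence to the food plan. The error is (M − L)/9: about 0.2 points for an on-plan mean of 4 and an assumed lead-in score of 2, never more than 0.67 points too low, zero if the two are equal, and an overstatement if the lead-in score is higher.

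This rests on the lead-in being week 1 of the nine, which is well supported but inferred, and on eight on-plan weeks, which is approximate because visit dates may move. If the lead-in came before the nine weeks, the mean would be sound and the text would only need to say so.

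The primary feasibility outcomes are untouched. The correction is still worth making before analysis: E.9 states a rule that targets the wrong period, and the remedy needs no new data.

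**What to change.** In E.9, Specific Aim 2:

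- Compute the mean weekly adherence score from the start of the food plan, excluding the lead-in week (weeks 2-9 if the lead-in is week 1).
- Use the same starting point for the percentage of days, the number of weeks and the 75%-of-days measure, so that all four cover one period.
- Report the lead-in week's score separately as the baseline value.
- Keep the lead-in week in the food-tracking adherence measures, since participants are asked to log during it.

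The cost is a few sentences in E.9, with matching wording in E.5 and E.6 where needed. Visits, data collection and participant burden do not change.
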